2. STUDY OBJECTIVES

2.1. PRIMARY OBJECTIVE

To evaluate the long-term safety and tolerability of flexibly dosed SEP-363856 (25, 50, or 75 mg/day [ie, once daily]) in adult subjects with schizophrenia who have completed Study SEP361-201 by the incidence of overall adverse events (AEs), serious AEs (SAEs), and AEs leading to discontinuation.

2.2. SECONDARY OBJECTIVES

- To evaluate the long-term safety and tolerability of SEP-363856 by assessing vital signs, physical examinations (PE), body weight and body mass index (BMI), 12-lead electrocardiograms (ECG), clinical laboratory evaluations, and suicidal ideation and suicidal behavior using the Columbia – Suicide Severity Rating Scale (C-SSRS)
- To evaluate the long-term effectiveness of SEP-363856 using the Positive and Negative Syndrome Scale (PANSS) total score, Clinical Global Impression-Severity (CGI-S), PANSS subscale scores (positive, negative, general psychopathology), Brief Negative Symptom Scale (BNSS), and Montgomery-Asberg Depression Rating Scale (MADRS)
- To explore the long-term maintenance of response in subjects treated with SEP-363856 as measured by the time to relapse and the rate of relapse

2.3. OTHER OBJECTIVES

- To assess whether long-term treatment with SEP-363856 is associated with extrapyramidal symptoms as measured by the Barnes Akathisia Rating Scale (BARS), the Abnormal Involuntary Movement Scale (AIMS), and the Simpson-Angus Scale (SAS)
- To characterize the long-term effects of SEP-363856 as measured by the Drug Effects Questionnaire (DEQ)

Document: Documentation\SAP

Author:

Version Number:

Final V1.0

Version Date:

27FEB2019

Template No: CS_TP_BS016 Revision 4
Effective Date: 01Apr2016

Reference: CS_WI_BS005

Copyright © 2009, 2010, 2012, 2016 Quintiles Transnational Corp. All rights reserved.

The contents of this document are confidential and proprietary to Quintiles Transnational Corp. Unauthorized use, disclosure or reproduction is strictly prohibited.

- To characterize the subjective long-term effects of SEP-363856 on sleep as measured by the Pittsburgh Sleep Quality Index (PSQI)
- To explore the effects of SEP-363856 on cognition as assessed by the CogState Brief Battery (CBB) and the CogState Schizophrenia Battery (CSB)
- To explore the effects of SEP-363856 on functional outcomes as measured by the UPSA-B total score

3. STUDY DESIGN

[figure not shown]
3.1. GENERAL DESCRIPTION

This is a 26-week, multiregional, open-label extension study designed to evaluate the long-term safety and tolerability of SEP-363856 for the treatment of subjects with schizophrenia who have completed the 4-week double-blind treatment phase of Study SEP361-201.

Subjects who meet the entry criteria will transition immediately from study SEP361-201 at Visit 7. Subjects will attend an initial visit on Day 1 (same day as Visit 7 of study SEP361-201). During the SEP361-202 study period, clinic visits will occur as shown in Table 1 Scheduled of Assessments.

Study schematic is shown in Figure 1. All subjects will receive open-label SEP-363856 50 mg/day from Day 1 through Day 3. Beginning on Day 4, flexible dosing ranging from 25 to 75 mg/day is permitted, if deemed clinically necessary (for reasons of safety, tolerability, or efficacy) by the Investigator. On Day 4, subjects are permitted (but not required) to titrate up to 75 mg/day for reasons of efficacy, at an unscheduled visit. Thereafter, an increase in dose should occur at weekly intervals in increments of one dose level at a time to a maximum dose of 75 mg/day. Dose reduction for tolerability purposes is allowed at any time during the study.

Figure 1: Study Schematic

26 Weeks Open-label

Note: Titration up to 75 mg/day is permitted (but not required) on Day 4 for reasons of efficacy as an unscheduled visit.

Document: Documentation\SAP

Author:

Version Number:

Final V1.0

Version Date:

27FEB2019

Template No: CS_TP_BS016 Revision 4
 Effective Date: 01Apr2016

Reference: CS_WI_BS005

Copyright © 2009, 2010, 2012, 2016 Quintiles Transnational Corp. All rights reserved.

The contents of this document are confidential and proprietary to Quintiles Transnational Corp. Unauthorized use, disclosure or reproduction is strictly prohibited.

3.2. SCHEDULE OF EVENTS

Schedule of events can be found in Table 1.

Document: Documentation\SAP

Author:

Version Number:
Version Date:

Final V1.0
27FEB2019

Template No: CS_TP_BS016 Revision 4
Effective Date: 01Apr2016

Reference: CS_WI_BS005

Copyright © 2009, 2010, 2012, 2016 Quintiles Transnational Corp. All rights reserved.
The contents of this document are confidential and proprietary to Quintiles Transnational Corp. Unauthorized use, disclosure or reproduction is strictly prohibited.

Statistical Analysis Plan

Table 1. Schedule of Assessments

Study Visit Number Study Visit Week	Visit 1E ^a Baseline	Visit 2E Week 1	Visit 3E Week 2	Visit 4E Week 3	Visit 5E Week 4	Visit 6E Week 8	Visit 7E Week 12	Visit 8E Week 16	Visit 9E Week 20	Visit 10E Week 24	Visit 11E Week 26 or ET ^b	Visit 12E Week 27 Follow- up ^c EOS	
Study Visit Day	1	8 ± 2	15 ± 2	22 ± 2	29 ± 3	57 ± 3	85 ± 3	113 ± 3	141 ± 3	169 ± 3	183 ± 3	190 ± 2	
Obtain informed consent	X												
Review inclusion/exclusion criteria	X												
Dispense study drug ^d	X ^m	X	X	X	X	X	X	X	X	X			
Study drug accountability		X	X	X	X	X	X	X	X	X	X		
Telephone Contacts ^e		Telephone calls to the subjects will be made between Weeks 1 and 2 and at Weeks 5, 7, 9, 11, 13, 15, 17, 19, 21, 23, and 25. If subject appears to be symptomatic, an unscheduled visit will be made as early as possible. ^f											
Clinical and Laboratory Evaluations													
Adverse event (AE) monitoring	 Performed at Visit 7 of study SEP361-201 	X	X	X	X	X	X	X	X	X	X	X	
Prior/concomitant medication review		X	X	X	X	X	X	X	X	X	X	X	X
Physical and neurological examination					X	X		X			X		
Vital signs ^g		X		X	X	X	X	X	X	X	X	X	X
Weight (including BMI)		X		X	X	X	X	X	X	X	X	X	
Waist circumference		X		X	X	X	X	X	X	X	X	X	
Electrocardiogram (ECG)		X			X	X	X	X	X	X	X	X	
Clinical laboratory tests ^h		X			X				X			X	
Blood sample for POPPK ⁱ		X			X				X			X	
Urine drug screen ^j		X			X				X			X	
Urine β-hCG ^k		X	X	X	X	X	X	X	X	X	X	X	X
Positive and Negative Syndrome Scale (PANSS)		X	X	X	X	X	X	X	X	X	X	X	

Document: Documentation\SAP
Author:

Version Number:
Version Date:

Final V1.0
27FEB2019

Template No: CS_TP_BS016 Revision 4
Effective Date: 01Apr2016

Reference: CS_WI_BS005

Statistical Analysis Plan

Table 1. Schedule of Assessments (Continued)

Study Visit Number Study Visit Week	Visit1E ^a Baseline	Visit2E Week 1	Visit3E Week 2	Visit4E Week 3	Visit5E Week 4	Visit6E Week 8	Visit7E Week 12	Visit8E Week 16	Visit9E Week 20	Visit10E Week 24	Visit 11E Week 26 or ET ^b	Visit 12E Week 27 Follow- up ^c EOS	
Study Visit Day	1	8 ± 2	15 ± 2	22 ± 2	29 ± 3	57 ± 3	85 ± 3	113 ± 3	141 ± 3	169 ± 3	183 ± 3	190 ± 2	
Brief Negative Symptoms Scale (BNSS)	↓	X	X	X	X	X	X	X	X	X	X		
Clinical Global Impression – Severity (CGI-S)		X	X	X	X	X	X	X	X	X	X	X	
Montgomery-Asberg Depression Rating Scale (MADRS)		X	X	X	X	X	X	X	X	X	X	X	
Columbia Suicide Severity Rating Scale (C-SSRS)		X	X	X	X	X	X	X	X	X	X	X	X
Drug effects questionnaire (DEQ)												X	X
Abnormal Involuntary Movement Scale (AIMS) ¹		X	X	X	X	X	X	X	X	X	X	X	
Barnes Akathisia Rating Scale (BARS) ¹		X	X	X	X	X	X	X	X	X	X	X	
Simpson-Angus Scale (SAS) ¹		X	X	X	X	X	X	X	X	X	X	X	
Pittsburg Sleep Quality Index (PSQI)		X				X		X			X	X	X
Cogstate Cognition Battery (CBB)													
Cogstate Schizophrenia Battery (CSB)								X				X	
USPA-B	X						X				X		

Abbreviations: AE = adverse event; AIMS = Abnormal Involuntary Movement Scale; BARS = Barnes Akathisia Rating Scale; β-hCG = human chorionic gonadotropin; BNSS = Brief Negative Symptoms Scale; CGI-S = Clinical Global Impression – Severity; CBB = Cogstate Brief Battery; CSB = CogState Schizophrenia Battery; C-SSRS = Columbia Suicide Severity Rating Scale ; ECG = Electrocardiogram; ET = early termination; MADRS = Asberg Depression Rating Scale; SAS = Simpson-Angus Scale; PANSS = Positive and Negative Syndrome Scale; PK = pharmacokinetic; PSQI = Pittsburg Sleep Quality Index;

Document: Documentation\SAP
 Author:

Version Number:
 Version Date:

Final V1.0
 27FEB2019

Template No: CS_TP_BS016 Revision 4
 Effective Date: 01Apr2016

Reference: CS_WI_BS005

Statistical Analysis Plan

- ^a Results of assessments from Visit 7 (Week 4) of Study SEP361-201 will serve as Baseline assessments for the present study. NOTE: Subjects may be hospitalized for the first week of the present study if deemed appropriate by the Investigator.
 - ^b If a subject discontinues from the study, all Visit 11E procedures should be performed at the discontinuation visit, within 48 hours of last study dose.
 - ^c All subjects will have a safety follow-up visit 7 (\pm 2) days after their last dose of study drug.
 - ^d All study drug will be taken once daily in the evening by mouth.
 - ^e Telephone calls will be made by a member of the research staff to the subjects between scheduled study visits (between Weeks 1 and 2, and at Weeks 5, 7, 9, 11, 13, 15, 17, 19, 21, 23, and 25) to monitor clinical symptoms and adverse events. If subject appears to be symptomatic, an unscheduled visit will be made as early as possible.
 - ^f Procedures and assessments for unscheduled visit are: drug accountability, physical and neurological examination, vital signs, ECG, clinical laboratory tests, urine drug screen, PANSS, CGI-S, MADRS, BNSS, AIMS, BARS, SAS, and C-SSRS.
 - ^g Vital signs will include supine and standing measurements of blood pressure and heart rate and respiratory rate and temperature.
 - ^h Clinical laboratory tests include: hematology, serum chemistry, urinalysis, serum prolactin, glycosylated hemoglobin (HbA_{1c}), and glucose and lipid panel (subjects must be fasted [no food or drink except water at least 8 hours] prior to collection of blood samples for glucose and lipid panel).
 - ⁱ Blood samples for determination of plasma SEP-363856 and SEP-363854 concentrations will be collected at Visit 2E, 5E, 8E, and 11E (time and date of the 3 previous doses of study medication and the time of the blood sampling must be recorded). Time of food intake relative to study drug taken should be recorded.
 - ^j Urine drug screen may be ordered at other visits as deemed clinically appropriate. These results should be discussed with the Medical Monitor.
 - ^k Any positive urine β -hCG test should be confirmed by a serum β -hCG test.
 - ^l Unscheduled BARS, AIMS, and SAS scales should be administered if a subject develops extrapyramidal symptoms (EPS) requiring treatment.
 - ^m Titration up to 75 mg/day is permitted (but not required) on Day 4 for reasons of efficacy as an unscheduled visit. At the minimum Investigator will assess AEs, concomitant medications and perform drug accountability at Day 4 unscheduled visit, all other assessments are not required but permitted based on Investigators judgment.
- Note: With the exception of the DEQ and the USPA-B, all rating assessments will be performed by the rater using a tablet. In the event that a tablet is not available, the rating assessments will be performed by the rater using a paper version of the assessment.

Document: Documentation\SAP
 Author:

Version Number:
 Version Date:

Final V1.0
 27FEB2019

Template No: CS_TP_BS016 Revision 4
 Effective Date: 01Apr2016

Reference: CS_WI_BS005

3.3. Determination of Sample Size

All subjects who complete the 4-week double-blind treatment period of Study SEP361-201 are eligible. It is anticipated that approximately 180 subjects will enter this open-label extension study.

3.4. Method of Assigning Subjects to Treatment Groups

All subjects will receive flexible dosing with SEP-363856 (25, 50, or 75 mg/day).

3.5. Blinding

This an open-label study.

3.6. CHANGES IN THE CONDUCT OF THE STUDY

The first subject entered study SEP361-202 under protocol version 2.00 (23 June 2016). The protocol versions and amendments listed below were implemented after the enrollment of the first subject:

- Protocol version 3.00 (22-Mar-2017); Amendment 2.00 (22-Mar-2017)
- Protocol version 3.01 (17-Aug-2017); Non-substantial Amendment 1.00 (17-Aug-2017)
- Protocol version 4.00 (13-Oct-2017); Amendment 3.00 (13-Oct-2017)

3.7. CHANGES TO ANALYSIS FROM PROTOCOL

- The protocol specified that for subjects *assigned* to double-blind SEP-363856, clinical response will be evaluated using the Day 29 data of study 361-201, against the DB baseline, and for subjects *assigned* to double-blind placebo, clinical response will be evaluated using the Day 29 data of study 361-202, against the OL baseline. Rather than the randomized treatment assigned to subjects, the analysis will be based on the *actual treatment received* during study 361-201. In addition, rather than using different baselines based on 361-201 treatment, DB baseline will be used for all subjects rolling over to 361-202, irrespective of the treatment they received in 361-201.
- The protocol specified that PANSS response rate will be calculated based on the DB baseline for subjects assigned to double-blind SEP-363856 and the OL baseline for subjects assigned to double-blind placebo. Rather than using different baselines based on 361-201 treatment, DB baseline will be used for all subjects rolling over to 361-202, irrespective of the treatment they received in 361-201.

Document: Documentation\SAP

Author:

Version Number:

Final V1.0

Version Date:

27FEB2019

Template No: CS_TP_BS016 Revision 4
 Effective Date: 01Apr2016

Reference: CS_WI_BS005

- The protocol specified that the total score will be used as a summary measure of the subject's ratings on the Simpson-Angus Rating Scale (SAS). Rather than the total score, the mean score will be used, which is calculated as the average of the 10 item scores.
- The protocol specified that one relapse criterion is emergence of suicidal ideation, homicidal ideation and/or risk of harm to self or others. The term 'suicidal ideation' is to be replaced by 'suicidality' and the term 'homicidal ideation' replaced by 'homicidality'. This is because the search criteria for AEs and C-SSRS data that meet this relapse criterion (see appendix 3) cover both suicidal ideation and suicidal behavior, and both homicidal ideation and homicidal behavior.

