6.2. Secondary Endpoints

- Absolute values and changes from double-blind (DB) Baseline of Study SEP361-201 and open-label (OL) Baseline of Study SEP361-202 in clinical laboratory tests (hematology, serum chemistry, urinalysis, glucose and lipid panel, prolactin, glycosylated hemoglobin (HbA_{1c}))
- Absolute values and changes from DB Baseline of Study SEP361-201 and OL Baseline of Study SEP361-202 in clinical evaluations (vital signs body weight, BMI, blood pressure [supine and standing], heart rate [supine and standing], 12-lead ECGs)
- Frequency and severity of suicidal ideation and suicidal behavior using the C-SSRS
- Rate of relapse and time to relapse during the 26-week OL period for subjects who demonstrated a clinical response to 4 weeks of treatment with SEP-363856. Relapse will be defined as the onset of any of the following:
 - An increase in PANSS total score $\geq 30\%$ from the PANSS total score at clinical response and a CGI-S score ≥ 3
 - Re-hospitalization for worsening of psychosis
 - Emergence of suicidal ideation, homicidal ideation and/or risk of harm to self or others.
- Changes from DB Baseline of Study SEP361-201 and OL Baseline of Study SEP361-202 in PANSS total score and subscale scores (positive, negative, and general psychopathology)
- Change from DB Baseline of Study SEP361-201 and OL Baseline of Study SEP361-202 in CGI-S score.
- Change from DB Baseline of Study SEP361-201 and OL Baseline of Study SEP361-202 in BNSS total score.
- Change from DB Baseline of Study SEP361-201 and OL Baseline of Study SEP361-202 in MADRS total score.
- Proportion of subjects who achieve a response, defined as a 20% or greater improvement in PANSS total score from the baseline, and calculated using (1) the DB Baseline of Study SEP361-201 for subjects assigned to double-blind SEP-363856, and (2) the OL Baseline of Study SEP361-202 for subjects assigned to double-blind placebo.

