15.3.5. Efficacy Analyses

Efficacy data will be summarized descriptively for the safety population.

The absolute values of PANSS total score and subscale scores (positive, negative, and general psychopathology), CGI-S score, BNSS total score, and MADRS total score at both the DB baseline of study SEP361-201 and OL baseline of study SEP361-202, and at each scheduled post-baseline extension visit, will be summarized descriptively.

Changes from baseline in the above efficacy measures will be summarized at each scheduled post-baseline extension visit, based on both the DB baseline of study SEP361-201 and the OL baseline of study SEP361-202.

PANSS total score and CGI-S score data will also be separately summarized by age group, gender, race, and geographic region (i.e. US sites vs. non-US sites). Additional subgroup factors and details of the subgroup analysis will be provided in SAP.

The proportion of subjects who achieve a response, defined as a 20% or greater improvement (i.e. decrease) in PANSS total score from the baseline at the end of the 26-week open-label extension period, will be calculated based on: (1) the DB baseline of study SEP361-201 for subjects assigned to double-blind SEP-363856, and (2) the OL baseline of study SEP361-202 for subjects

assigned to double-blind placebo. For subjects who discontinue early, the PANSS total score measured at the early termination visit will be used.

The CBB composite score at the DB baseline of study SEP361-201 and OL baseline of study SEP361-202 will be calculated. The composite score based on the four domains contained in the CBB scale (i.e. attention, information processing, visual learning, and working memory) will be calculated from the CSB assessment result at Visit 7E (Week 12) and Visit 11E (Week 26) of study SEP361-202. The composite score of CSB at Visits 7E and 11E will also be calculated.

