16.1.5. PROPORTION OF SUBJECTS WHO ACHIEVE A RESPONSE

PANSS response is defined as a 20% or greater improvement (i.e. decrease) in PANSS total score from the DB baseline to the Week 26 LOCF endpoint.

The percent change in PANSS total score from baseline will be calculated by:

$$\frac{\text{PANSS total score at the Week 26 LOCF endpoint} - \text{PANSS total score at DB baseline}}{\text{PANSS total score at DB baseline} - 30} \times 100\%$$

For each subject, the responder indicator will be set to 1 if the percent change as calculated above is <= -20%. The indicator will be set to 0 if the percentage is > -20%. The indicator will be set to missing if the percentage is missing.

The proportion of subjects who achieve a PANSS response will also be calculated for each scheduled post-OL baseline extension visit (i.e. Week 1/Visit 2E through Week 26/Visit 11E) using a similar method as above.

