16.2.3. OBSERVED VALUES AND CHANGE FROM BASELINE IN BNSS TOTAL SCORE

The BNSS is a rating scale to measure the current level of severity of negative symptoms in schizophrenia and schizoaffective disorder. The measure is comprised of 13 individual items organized in 6 subscales (blunted affect (items 9, 10, 11), alogia (items 12, 13), avolition (items 7, 8), anhedonia (items 1, 2, 3), asociality (items 5, 6), and distress (item 4)). Each of the items are scored on a Likert-type 7-point scale from 0 - 6, where values of 0 indicates symptom is absent and a value of 6 means the symptom is a severe form. The 13 individual items provide a composite total score (ranging from 0 to 78). In addition BNSS subscale scores will be calculated by summing the item scores under each subscale. If any item score contributing to the total score or a subscale score is missing or rated as "9" (i.e. not rated), then the BNSS total score or the subscale score will be set to missing.

The observed values of BNSS total score at both the DB baseline and the OL baseline, and at each scheduled post-OL baseline extension visit and LOCF, will be summarized descriptively.

Changes from baseline in BNSS total score will be summarized for each scheduled post-OL baseline extension visit and LOCF, based on both the DB baseline and the OL baseline.

A sensitivity analysis for BNSS will be performed where a BNSS subtotal score will be calculated by summing the scores of items 1-6 and 8-13. Item 7 (Avolition: Behavior) is excluded due to several subjects being given a score of '9' for this item when '9' is not a valid rating. Among the 12 items contributing to BNSS subtotal score, if any item is rated as '9', the subtotal score will be set to missing. The same analyses performed on BNSS total score will be repeated on BNSS subtotal score.

16.2.4. OBSERVED VALUES AND CHANGE FROM BASELINE IN CBB COMPOSITE SCORE AND OBSERVED VALUES AND CHANGE FROM OL WEEK 12 IN CSB COMPOSITE SCORE

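### The SAP measures PANSS response in prior-placebo subjects from the double-blind baseline without giving a reason and keeps no response rate from the protocol's open-label baseline, so change on placebo enters the PBO-SEP and ALL EXT rates

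*SAP*

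**What the plan says.** **Protocol.** The synopsis, 6.2 and 15.3.5 define this secondary endpoint in the same way: a fall of at least 20% in PANSS total score. Subjects randomised to SEP-363856 in the parent study are measured from the DB baseline. The others are measured from "the OL Baseline of Study SEP361-202 for subjects assigned to double-blind placebo". Each group is thus measured from its own start of active drug.

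**SAP 3.7, second bullet.** The SAP restates the rule ("The protocol specified that PANSS response rate will be calculated based on the DB baseline for subjects assigned to double-blind SEP-363856 and the OL baseline", the latter applying to prior-placebo subjects) and then replaces it: "DB baseline will be used for all subjects rolling over to 361-202, irrespective of the treatment they received in 361-201". The same sentence closes the bullet before it, which concerns entry to the relapse population. The point here is about the second bullet only.

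**SAP 16.1.5 and 16.1.6.** Response is improvement "in PANSS total score from the DB baseline to the Week 26 LOCF endpoint", and "the responder indicator will be set to 1 if the percent change as calculated above is <= -20" percent. The same method is used at each extension visit from Week 1. The cumulative curve in 16.1.6 also uses the DB baseline only.

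**What remains from the OL baseline.** SAP 16.1.1 summarises observed PANSS totals at both baselines and mean changes from both, by visit and at LOCF. SAP Appendix 1 displays PBO-SEP, SEP-SEP and ALL EXT separately. The SAP text specifies no response proportion from the OL baseline.

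**The concern.** For a prior-placebo subject, the interval from DB to OL baseline is the four-week placebo phase of the parent study. Taking the DB baseline as reference puts that interval inside the response calculation. Some PBO-SEP subjects can then meet the definition before their first dose of open-label drug and keep it with no further change.

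The objective in Protocol 5.2 and SAP 2.2 is the long-term effectiveness of SEP-363856, so the PBO-SEP and ALL EXT response rates are likely to be read in that light. Under the protocol's rule the PBO-SEP rate covered time on drug only. Under the SAP's rule it covers placebo and drug together, and the reader has no responder figure that separates the two. SAP 3.7 does give a reason for its change to the suicidality relapse criterion, but none for this one.

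**Working it through.** The documents contain no expected response rate or sample-size calculation for this endpoint, so there is no stated figure to reproduce.

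**1. Formula.** From SAP 6.7 and 16.1.5: percent change = 100 × (score − baseline) / (baseline − 30), with response at −20% or lower. The fall needed is 0.20 × (baseline − 30):

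- baseline 80: 0.20 × 50 = 10 points
- baseline 100: 0.20 × 70 = 14 points
- baseline 120: 0.20 × 90 = 18 points

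A prior-placebo subject who falls this far on placebo is a responder under SAP 16.1.5 with no change on open-label drug.

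**2. Single subjects, same formula, two baselines.**

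| DB | OL | Endpoint | From DB (SAP) | From OL (protocol baseline) |
|---|---|---|---|---|
| 100 | 86 | 86 | −14/70 = −20.0%, responder | 0/56 = 0.0%, non-responder |
| 100 | 80 | 84 | −16/70 = −22.9%, responder | +4/50 = +8.0%, non-responder |
| 100 | 110 | 94 | −6/70 = −8.6%, non-responder | −16/80 = −20.0%, responder |

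The second subject is worse on open-label drug. The third shows that the switch can also work the other way.

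**3. Further fall needed on drug.** With DB baseline B and a placebo-phase fall f, the SAP rule needs 0.20 × (B − 30) − f more points. The OL rule needs 0.20 × (B − f − 30). The difference is 0.8 × f. For B = 100 and f = 10 this is 4 points against 12. The minus-30 term is the SAP's; the protocol states only a 20% improvement. On the raw total the same subject needs 0.20 × 100 − 10 = 10 points against 0.20 × 90 = 18. The thresholds depend on the scale, but the 8-point gap does not.

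**4. Group rates, illustrative only.** The documents give no PANSS means, SDs or placebo-phase changes. Assumed values: DB baseline normal with mean 100 and SD 9; independent normal changes in each phase, SD 12 or 16; mean open-label change 0, −5, −10 or −15; 400,000 simulated subjects per scenario. Response rate from DB minus response rate from OL, in PBO-SEP:

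| Assumed mean placebo-phase change | Difference, percentage points |
|---|---|
| 0 | −0.9 to +7.7 |
| −5 | +5.5 to +15.2 |
| −10 | +11.3 to +24.3 |
| −15 | +16.3 to +33.6 |

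For example, with a mean change of −10 in both phases the rates are 63.9% against 43.7% (SD 12) and 60.2% against 45.0% (SD 16).

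**5. ALL EXT.** The placebo share of the roughly 180 subjects is not given. If it is one third to one half, a 20-point gap in PBO-SEP moves the pooled rate by 20 × 1/3 = 6.7 to 20 × 1/2 = 10 points.

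**The case against.** The strongest defence has four parts.

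- **The change is declared and nothing is tested.** Protocol 4.4 rules out hypothesis tests, so no error rate is at stake. This stands. What is affected is the meaning of a descriptive rate.
- **The effect is visible elsewhere.** Separate columns and mean changes from both baselines let a reader see the average placebo-phase and open-label change in PBO-SEP. This stands and limits the harm. A mean does not give back a responder proportion, however, and the PBO-SEP column itself carries the altered rate.
- **A common baseline has a use.** It puts every subject on one reference point and describes total improvement since entry to the parent study. The protocol's pooled rate combines about 30 weeks for SEP-SEP with 26 for PBO-SEP. This stands as a reason to keep the DB-baseline figure, but not as a reason to drop the other.
- **The OL baseline does not isolate a drug effect.** In an uncontrolled extension, non-drug improvement enters either rule, including the protocol's own DB-baseline rule for SEP-SEP. This also stands. The OL baseline removes only the placebo phase.

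Two stronger readings are tempting. A reader might infer that the SAP calls this rate response to SEP-363856. SAP 16.1.5 says only PANSS response; the attribution to drug is in SAP 5.2, for the relapse population. A reader might also infer from SAP 16.2.3, where "Item 7 (Avolition: Behavior) is excluded due to several subjects being given a score of" 9, that the baseline was chosen after seeing results. That passage concerns invalid codes on one BNSS item. It does not show that PANSS response had been examined or that it influenced this choice.

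**Conclusion.** The point holds as a disclosed but unexplained replacement of half of a secondary endpoint. The SEP-SEP baseline is unchanged; the PBO-SEP rate, and through it ALL EXT, no longer measures what the protocol defined. That placebo-phase change enters these rates follows from the formula and needs no assumption.

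Direction and size are conditional. If the placebo phase shows mean improvement, the PBO-SEP rate is expected to be higher than under the protocol: roughly 6 to 34 percentage points for assumed mean changes of −5 to −15. With zero mean change the difference is about −1 to +8. A reader might infer that the rate is certainly inflated, or by a known amount. The documents support neither, because they give no placebo-phase data and individual subjects can move either way. The matter is worth correcting because the remedy is cheap, but it does not threaten the study's primary safety objective.

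**What to change.** - In SAP 16.1.5, at Week 26 LOCF and by visit, add the protocol-defined response beside the DB-baseline figures: OL baseline for PBO-SEP, DB baseline for SEP-SEP, and the resulting ALL EXT rate. Use the SAP 6.7 formula for both sets so that only the baseline differs.
- Label the DB-baseline PBO-SEP and ALL EXT figures as including four weeks of placebo for prior-placebo subjects.
- State in SAP 3.7 why the baseline was changed.

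Showing both pooled rates avoids having to choose between a common baseline and the protocol's definition. The OL-baseline PANSS is already defined in SAP 6.2 and used in 16.1.1, so the cost is one derived flag and a few table rows, and a PBO-SEP figure that may be less favourable.
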